4. Presence of hypertrophic cardiomyopathy
5. Presence of infiltrative/restrictive cardiomyopathy
6. Echocardiographic evidence of moderate or severe aortic or mitral valve stenosis or regurgitation
7. Bioprosthetic or mechanical valves
8. Use of medication that effect folate metabolism (e.g. Methotrexate, pralatrexate)
9. Previously diagnosed phenylketonuria
10. Previously diagnosed BH4 deficiencies
11. End stage renal disease requiring hemodialysis
12. Pre-existing seizure disorder
13. Terminal illness (not including heart failure) with expected survival of one year or less
14. Females who are pregnant or breastfeeding. All females of child bearing age will undergo pregnancy testing prior to randomization.
15. Recent hospitalization within three months.

Source of Participants and Participant Recruitment:

Patient recruitment will occur at the site of the Providence VAMC by echocardiographic database and medical chart search. A population of potential study patients will be generated, which will identify patients with echocardiographic parameters of diastolic dysfunction without evidence of systolic dysfunction. Subsequently, a chart review of the electronic medical record system [CPRS] will be performed on potential patients to evaluate for inclusion and exclusion criteria. Potential subjects will be temporarily recorded in a password protected spreadsheet in a restricted access folder on a VA secure server. Personal identifiers of subjects who do not participate will be deleted from the database. We will be requesting an IRB waiver of HIPAA and informed consent for screening purposes ONLY.

After subjects are identified by screening of the database and chart review, subjects will be sent a letter informing about the study. The letter will contain a return envelope to notify us within 15 days of the mailing date if the subject does not want to be contacted by phone. If we do not receive the refusal letter, subjects will be contacted by telephone and will be provided basic information regarding the study. Patients who are interested in participating will be scheduled for a screening visit.

Study Visits (Total of 7 Study Visits and 5 Telephone Calls)

The study visits will take place in patient exam rooms in either the main hospital (building 1), research buildings 32 or 35.

1. Screening visit:

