Members of the investigator team will explain the study to the potential participants and answer any questions that they may have regarding the study protocol. The investigator will make it clear that the protocol is research as well as voluntary and that declining participation will in no way affect further evaluation or access to clinical care. Participants will also be informed that they may withdraw their consent at any point throughout the study. Patients will be given adequate time to read the consent form and discuss its contents with research personnel before signing the consent form. They will also be provided with a phone number through which adverse events should be reported. Participants will then be asked to sign an IRB-approved written consent document and health insurance portability and accountability act (HIPAA) agreement, which will allow data pertinent to the study to be collected.

Following the completion of informed consent, the baseline visit will be scheduled within one week of study enrollment.

2. Baseline visit:

At this visit, the subjects will undergo a brief interview to assess for recent changes in health status. Cardiopulmonary exercise testing will be performed to establish the subjects' baseline. The patients will then be randomized (in a 1:1 fashion as mentioned above) to either Group 1, who will begin the study by taking the study medication in addition to their current medication regimen, or Group 2, who will begin the study by continuing their current medication regimen without the study medication. The subjects in Group 1 will be provided with their preference of either a supply of 100mg Kuvan®(sapropterin dihydrochloride) tablets or Kuvan®(sapropterin dihydrochloride) in the powder form. This visit will last three hours.

The subjects in Group 1 will be instructed to initiate the study medication at the weight-based dose of 10mg/kg (rounded to the nearest hundred) with meals (at the same time each day) for one week beginning the following day (day 1). After telephone contact (table 2) with a study team member on day 7, assuming no adverse effects are noted, the patient will be instructed to increase their daily dose to 20mg/kg (rounded to the nearest hundred) with meals (at the same time each day) for the remainder of the study period. The subjects in Group 2 will not be started on the study medication until after the 'wash-out period' as described in the study design

Study Drug:

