Kuvan®(sapropterin dihydrochloride) is the synthetic form of the naturally occurring essential cofactor BH4 that is FDA approved for the treatment of phenylketonuria at the recommended dose of 10-20mg/kg daily. This study **does not require an IND waiver** as set forth by the **FDA guidelines listed below:**

"The clinical investigation of a drug product that is lawfully marketed in the United States is exempt from the requirements of this part [investigational new drug application] if all the following apply:

- (i) The investigation is not intended to be reported to FDA as a well-controlled study in support of a new indication for use nor intended to be used to support any other significant change in the labeling for the drug;*
- (ii) If the drug that is undergoing investigation is lawfully marketed as a prescription drug product, the investigation is not intended to support a significant change in the advertising for the product;*
- (iii) The investigation does not involve a route of administration or dosage level or use in a patient population or other factor that significantly increases the risks (or decreases the acceptability of the risks) associated with the use of the drug product;*
- (iv) The investigation is conducted in compliance with the requirements for institutional review set forth in part 56 and with the requirements for informed consent set forth in part 50; and*
- (v) The investigation is conducted in compliance with the requirements of 312.7."*

The study drug will be provided by BioMarin (Committee decision letter attached below – Appendix A)

Compliance will be assessed by monitoring pill counts with the assistance of the research pharmacist.

Follow up visits:

Patients will attend routine follow up visits as outlined below. These visits will occur within one week of the proposed outlined schedule. At all study visits, a brief history and physical exam will be performed and subjects will be evaluated for medication compliance, adverse reactions, and exacerbation history. In addition, interim ED visits and hospitalizations will be assessed for. Any exacerbations of heart failure, defined as worsening in dyspnea (including orthopnea or paroxysmal nocturnal dyspnea), Jugular Venous Pressure elevation, significant weight gain (>3 lbs in 3 days) or lower extremity edema will be recorded.

Summary of follow up visits is as follows:

6 week visit (thirty minutes) – Brief history and physical exam

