12 week visit (three hours)- Brief history and physical exam, Kansas City Cardiomyopathy Questionnaire, labwork for biomarkers (as documented above), chemistry, lipid, and liver panels, BNP, echocardiogram, and CPET testing.

13 week visit (thirty minutes)- Patients will be crossed over to the second arm of the study. They will receive a brief history and the second group will be provided with a supply of Kuvan®(sapropterin dihydrochloride) tablets or powder.

19 week visit (thirty minutes)- Brief history and physical exam.

25 week visit (three hours)- Brief history, Kansas City Cardiomyopathy Questionnaire, labwork for biomarkers, chemistry, lipid, and liver panels, BNP, echocardiogram, and CPET testing.

Telephone calls will be made at week 1, 3, 9, 16, and 22 to assess for patient compliance, provide any necessary support, and screen for side effects.

	Screening Visit	Baseline Visit	Week 1	Week 3	Week 6	Week 9	Week 12	Week 13	Week 16	Week 19	Week 22	Week 25
Contact	Clinic	Clinic	Tel	Tel	Clinic	Tel	Clinic	Clinic	Tel	Clinic	Tel	Clinic
Limited History/Physical	x				x		x	x		x		x
Assess Medication Compliance					x		x			x		x
Labwork	x						x					x
Echo	x						x					x
CPET		x					x					x
KCCQ	x						x					x
Exacerbation History		x	x	x	X	x	x	x	x	x	x	x
Adverse Event Monitoring			x	x	X	x	x	x	x	x	x	x

Table 1. Follow-up Clinic Visits, telephone calls, and schedule of studies. CPET, cardiopulmonary exercise stress test; KCCQ, Kansas City Cardiomyopathy questionnaire; Tel, telephone contact; Labwork: basic chemistry panel, complete blood count, lipid panel, liver function tests, and the following biomarkers: BNP, glutathionylated myosin binding protein C, adiponectin, aldosterone, endothelin-1, NT-procollagen III, uric acid, DROM

Subject Reimbursement:

Subjects will be reimbursed for every visit they attend. Attendance to visits 1 and 2 (screening and baseline visits), as well as visits 4 and 7 (all three hour visits) will be reimbursed fifty dollars. Attendance to visits 3, 5, and 6 will be reimbursed twenty-five dollars.

Specific Study Procedures:

Questionnaire: The Kansas City Cardiomyopathy questionnaire will be used and is attached (Appendix B).

Echocardiogram: Transthoracic echocardiography uses ultrasound technology to evaluate heart structure and function. Measurements to be collected include:

1. Tissue Doppler Index (Septal and Lateral E')
2. E Velocity
3. E/E' ratio
4. E/A Ratio
5. Pulmonary Vein Tracing (S/D Ratio, A-AR duration, AR Velocity)

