Patients will be contacted via phone at weeks 1, 3, 9, 16, and 22. During these phone calls, patients will be asked the questions outlined in Table 2. Additionally, the patients will be seen in person in a research clinic during weeks 6, 12, 13, 19, and 25. At these clinic visits, patients will be asked the questions listed in Table 3. The research team will meet every 4 weeks to review study progress and adverse events. Additionally, all data will be reviewed to assure that no physiological findings warrant immediate intervention. If so, the participant will be contacted and advised of the findings and offered assistance with appropriate referrals. Data from the echocardiogram, laboratory tests and cardiopulmonary exercise testing procedures will be reviewed by the investigators and any unusual or adverse findings will be communicated to the participant's primary care physician. Adverse events will be defined as per the BioMarin Standard Language for Adverse Event Report (below, and attached in Appendix D) and reported to the IRB in accordance with the rules regulating each severity class (expected vs. unexpected, serious vs. other, related vs. unrelated).

BioMarin Standard Language for Adverse Event Reporting: IST Program, Kuvan

According to the ICH definition, an adverse event (AE) is any untoward medical occurrence in a patient or clinical investigation subject administered a pharmaceutical product, and that does not necessarily have a causal relationship with this treatment. An AE can therefore be any unfavorable and unintended sign (including an abnormal laboratory finding), symptom, or disease temporally associated with the use of a medicinal (investigational) product, whether or not considered related to the investigational product.

This definition includes intercurrent illnesses or injuries that represent an exacerbation (increase in frequency, severity, or specificity) of pre-existing conditions. Whenever possible, it is preferable to record a diagnosis as the AE term rather than a series of terms relating to a diagnosis.

Adverse event information will be collected in an ongoing fashion through patient reporting AEs to their physician or health care provider. Seriousness and relatedness will be assessed by the treating physician, with appropriate reporting.

A designated primary contact person based at the treatment center will be responsible for the collection and reporting of AEs for patients participating in the program.

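### Group 2 starts drug at week 13 with no written dose or titration and no scheduled contact until week 16, whereas Group 1 may double its dose only after a day-7 call

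*Combined protocol and SAP*

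**What the plan says.** Under the Baseline visit, Group 1 takes 10 mg/kg daily for one week from the day after that visit. The increase to 20 mg/kg is conditional: "After telephone contact (table 2) with a study team member on day 7, assuming no adverse effects are noted".

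For Group 2 the same section addresses only timing: "The subjects in Group 2 will not be started on the study medication until after the" wash-out. The 13 week visit entry in the summary of follow-up visits says "Patients will be crossed over to the second arm of the study", and then "They will receive a brief history and the second group will be provided with a supply of" tablets or powder. Neither place gives Group 2 a dose, a titration step or a check before escalation. The other doses in the protocol are the 10 mg/kg test dose at screening and the approved phenylketonuria doses, and neither is a dosing instruction for Group 2.

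The call schedule is the same wherever it appears. The summary of follow-up visits has "Telephone calls will be made at week 1, 3, 9, 16, and 22", Data and safety monitoring has "Patients will be contacted via phone at weeks 1, 3, 9, 16, and 22", and Table 1 shows the same five weeks. The Study Visits heading gives the totals: "Total of 7 Study Visits and 5 Telephone Calls". On timing, the Follow up visits section states "These visits will occur within one week of the proposed outlined schedule".

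**The concern.** The protocol makes a call with no adverse effects the condition for doubling the dose, then provides that call for only one of the two sequences. Therapeutic risks mentions hypersensitivity, including anaphylaxis, and places most such reactions soon after treatment starts. Half the subjects pass through that period, and possibly a dose doubling, without the scheduled check that the other half receives.

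There is also a question of what Group 2 actually takes. With nothing written, staff must decide for themselves when Group 2 doubles. The crossover analysis of peak VO₂ combines drug periods from both sequences, so the regimen should be the same in each. If staff waited for the next scheduled call, it would not be.

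**Working it through.** **Reproduce the plan's own count.** Clinic contacts in Table 1 are screening, baseline and weeks 6, 12, 13, 19 and 25, which makes 7. Telephone contacts are weeks 1, 3, 9, 16 and 22, which makes 5. Both agree with the stated totals, so a week 14 call has not simply been lost from the text.

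**Match the on-drug contacts.** Group 1's contacts after starting drug are at weeks 1, 3, 6, 9 and 12. Group 2 receives drug at week 13, so its counterparts are those weeks plus 13:

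| Group 1 week | Plus 13 | In schedule? |
|---|---|---|
| 1 (titration call) | 14 | No |
| 3 | 16 | Yes |
| 6 | 19 | Yes |
| 9 | 22 | Yes |
| 12 | 25 | Yes |

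Group 1 has 5 scheduled contacts in 12 weeks on drug and Group 2 has 4.

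**Time to first scheduled contact.** Group 2's first dosing day is not stated. I assume it is the day after the week 13 visit, as in Group 1 after baseline.

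- Group 1: day 7.
- Group 2, nominal: 16 − 13 = 3 weeks, or day 21.
- Group 2, with the week 13 visit one week late and the call held at week 16: 16 − 14 = 2 weeks, or 14 days.
- Group 2, with that visit one week early: 16 − 12 = 4 weeks, or 28 days.

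In the first 13 days on drug, Group 1 has 1 scheduled contact and Group 2 has 0, wherever the week 13 visit falls in its window. These are times to a scheduled contact, not times to detection of a reaction.

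**Subjects affected.** 30 subjects randomized 1:1 gives 30/2 = 15.

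**Possible effect on dose.** Group 1 has 12 − 1 = 11 weeks at 20 mg/kg before its on-drug exercise test. If Group 2 doubled at the week 16 call, it would have 25 − 16 = 9. Planned cumulative dose over 84 days in Group 1 is 7 × 10 + 77 × 20 = 1610 mg/kg. For Group 2 it depends on what staff do:

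- Unscheduled doubling at day 7: 1610 mg/kg (no difference).
- Doubling at the week 16 call: 21 × 10 + 63 × 20 = 1470 mg/kg (1470/1610 − 1 = −8.7%).
- Starting directly at 20 mg/kg: 84 × 20 = 1680 mg/kg (+4.3%).
- Never increasing: 84 × 10 = 840 mg/kg (−47.8%).

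The last is a lower bound that nothing in the protocol suggests is intended.

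**The case against.** The strongest reply is that Group 2's regimen is implied. In a crossover, moving to the other arm means taking the regimen already defined, and day 7 counts from the first dose, so the call comes with it. That is probably what was meant. But on that reading a day-7 call is required, and a schedule stated consistently in several places does not contain one. Staff could make an unscheduled call, but no text requires it.

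Second, there are other safeguards. Every subject has an observed 10 mg/kg test dose at screening, and those who react go no further. Subjects are given a number for reporting events, staff check records for emergency visits and hospitalizations, the team reviews adverse events every 4 weeks, and 20 mg/kg is within the approved phenylketonuria range. These points lower the risk. However, Group 1 has the same safeguards and still gets the call. The test dose is observed for one hour only and comes about 13 weeks or more before Group 2's daily dosing. The record check would miss milder effects that ought to hold back an increase.

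Third, a day-7 call is a weak defence against reactions in the first days, and the side-effect prompts in Table 2 do not include rash, itching or swelling. This is fair. The call's main value is as a check before escalation, and the concern rests chiefly on that.

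Fourth, the 28-day bound needs the crossover visit at week 12. With a one-week wash-out, the end-of-period visit would then also have to come early. That is correct, so the nominal 21 days is the figure to rely on. The 14-day bound does not need this condition.

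Finally, different exposure between sequences is only a possibility, and the documents do not show that it would change peak VO₂. That also stands.

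**Conclusion.** The concern holds. About 15 of 30 subjects begin daily drug with no written dose or titration. Their first scheduled contact is at about day 21, against day 7 in Group 1. The contact missing from their schedule is the one that controls Group 1's dose increase. Because the other four contacts match exactly, this looks like an oversight, and the protocol gives no reason for the omission.

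The gap in the schedule is certain. The 21 days assumes that Group 2 starts the day after a week 13 visit held on time, and the 14 to 28 day range assumes that the visit moves within its window while the call does not. Two weeks fewer at 20 mg/kg (9 against 11) is a possible consequence, conditional on staff waiting for week 16. The change should be made, because it restores a safety check that the protocol itself treats as necessary.

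**What to change.** Add one telephone call to both groups, 7 days after the actual week 13 visit (week 14 on the nominal schedule), using the Table 2 questions and with an Adverse Event Monitoring mark in Table 1. Tie it to the visit date: a call fixed at calendar week 14 could fall anywhere from 0 to 14 days after a week 13 visit that moves by up to one week. Calling both groups keeps contact equal, as the existing calls do. Calling Group 2 alone would close the safety gap with 15 calls.

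State that Group 2 takes 10 mg/kg from the day after the week 13 visit and goes to 20 mg/kg only after this call finds no adverse effects. Both sequences would then have contacts at 1, 3, 6, 9 and 12 weeks on drug and a planned 1610 mg/kg over 84 days. If the call is also meant to pick up hypersensitivity, Table 2 needs a prompt for it.

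The cost is 30 × 1 = 30 short calls, one extra column and a few marks in Table 1, a change from 5 to 6 calls under Study Visits, and wording edits in the Baseline visit, the summary of follow-up visits and Data and safety monitoring. No visit or procedure is added and eligibility is unchanged.

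As a separate clerical correction, Table 1 could mark Adverse Event Monitoring at screening, where subjects are observed for reactions to the test dose, and at baseline, which the Monitoring for Adverse Events section covers.

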At this visit, the study will be explained in detail to the patient, and inclusion and exclusion criteria will be reviewed by the study team members. If the patient meets the eligibility criteria and is willing to participate, written informed consent will be obtained. Following the completion of informed consent, the subjects will undergo a limited history and physical exam.

Blood will be drawn for measurement of basic chemistry panel, complete blood count, fasting lipid panel, liver function tests, and the following biomarkers: BNP, glutathionylated myosin binding protein C, adiponectin, aldosterone, endothelin-1, NT-procollagen III, uric acid, and derivatives of reactive oxygen metabolites (DROM). These blood tests have been examined in various studies as markers of the presence of heart failure, ability to respond to treatment of heart failure, or early diagnosis of heart failure¹¹⁻¹⁵.

Subjects will then receive a weight-based test dose of 10mg/kg (rounded to the nearest hundred) of the study medication (Kuvan®(sapropterin dihydrochloride),) and the subject will be observed with blood pressure and oxygen levels being recorded every thirty minutes for one hour. If at any point during this time period, the subject develops hypotension (Systolic Blood Pressure [SBP] <90 or a drop in SBP >20mmHg with associated dizziness or syncope), hypoxemia (decrease in oxygen saturation to <90% on room air), or any evidence of an allergic reaction (pruritus, rash, hives, Heart Rate>100, abdominal cramping, nausea, emesis, or angioedema), the subject will not participate further in the study. Subjects experiencing any of the above symptoms will receive appropriate monitoring and clinical care, potentially including hospital admission, supplemental oxygen, IV fluids, until they are stabilized.

The patients who tolerate the test dose will complete the Kansas City Cardiomyopathy Questionnaire and receive a baseline echocardiogram.

Informed Consent Procedure:

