Blood Samples Transfer see: Protocol Addendum: Information Privacy and Security Items and Safety

Patient safety:

Human Subjects Research

This Human Subjects Research meets the definition of “Clinical Research”. This study is a clinical trial, and will be registered on Clinicaltrials.gov.

Protection of human subjects

Potential risks

Questionnaires and record keeping. There is no specific physical risk to completing the quality of life questionnaires. All records will be kept confidential, kept in locked cabinets, and identified by study code only in the working databases.

Phlebotomy. Phlebotomy for blood drawing is associated with temporary pain at this site and may result in bruising at the needle insertion site. Risks of the procedure include: vasovagal reaction during needle puncture; bruising at the phlebotomy site; and the possibility of skin or soft tissue infection at the needle puncture site.

Echocardiogram. Standard approaches to performing transthoracic echocardiography will be utilized, which may induce transient discomfort as the ultrasound probe is pressed against the upper chest.

Cardiopulmonary exercise testing. The testing may cause shortness of breath, fatigue, muscle discomfort, and very rarely (<1:1,000) may be associated with heart attack or death.

Therapeutic risks

Treatment with Kuvan®(sapropterin dihydrochloride).

Kuvan®(sapropterin dihydrochloride) is currently FDA approved for the treatment of phenylketonuria (PKU). The most common side effects include: headache, peripheral edema, arthralgia, polyuria, agitation, dizziness, nausea, pharyngitis, abdominal pain, upper abdominal pain, and upper respiratory tract infection.

In clinical trials the most common adverse reactions ($\geq 4\%$ of patients) were: headache, rhinorrhea, pharyngolaryngeal pain, diarrhea, vomiting, cough, and nasal congestion.

In the postmarketing period, the most common adverse reactions due to Kuvan are oropharyngeal pain, pharyngitis, esophageal pain, gastritis, dyspepsia, abdominal pain, nausea and vomiting. Hypersensitivity reactions including anaphylaxis and rash have been reported. Most hypersensitivity reactions occurred within several days of initiating treatment. Two cases of hyperactivity have been reported, including one case in a patient who received an accidental overdose of Kuvan.

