All serious adverse events (SAEs) and pregnancy reports whether or not considered drug-related should be reported to BioMarin Pharmacovigilance within 24 hours of receipt by the investigator/sponsor by using the FDA 3500A (MedWatch Form). Clinicians should not wait to collect additional information that fully documents the event before notifying BioMarin's Pharmacovigilance Department of an SAE or pregnancy. BioMarin may be required to report certain SAEs to regulatory authorities within 7 calendar days of being notified about the event; therefore it is important that clinicians submit additional information requested by BioMarin Pharmacovigilance as soon as it becomes available.

Reporting of SAEs to the IRB will be done in compliance with the standard operating procedures and policies of the IRB and with applicable regulatory requirements.

Follow up visits:

Patients will undergo routine follow up visits as outlined in Table 1 to assess compliance with medication use, changes in symptoms, development of adverse reactions and further data collection.

Monitoring for Adverse Events (AEs)

At the baseline clinic visit and each follow-up contact, subjects are to notify study staff if they experience any change in their medical condition or medications, or have urgent care visits, emergency room visits, or hospitalizations. Study staff will also monitor for interim emergency room visits or hospitalizations through patient notification system in CPRS to ensure timely reporting. The investigator will contact participants if any reported adverse event suggests clinical deterioration warranting immediate medical attention. During the study, if a subject experiences medical problems or hospitalization, the study medication will be continued unless complicated by symptomatic hypotension. If discontinued, it would be resumed once baseline clinical status is confirmed, assuming the event was not felt to be related to the study medication itself.

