Any adverse events that are immediately life-threatening, cause permanent or lasting harm, or require a hospitalization will receive a “serious” classification as per defined by the BioMarin Standard Language for Adverse Event Report (above, and Appendix D). All serious AEs and unanticipated problems will be reported to the IRB as soon as possible, but no later than 5 days from notification. If an event is possibly, probably or definitely related to the intervention, it will be classified as intervention-related. Any incidental finding discovered during follow up visits or imaging will be graded based on level of severity. Severe findings (as determined by evaluating physician) will be referred to the Emergency Department for further evaluation. Findings determined to be low or moderate severity will be relayed to both the subject and his or her primary care physician or cardiologist.

Sample size determination**Primary Aim:**

This study is a pilot study, and as a result a sample size determination is not necessary.

Data Collected see: Protocol Addendum: Information Privacy and Security Items and Safety**Data Analysis Plan see: Protocol Addendum: Information Privacy and Security Items and Safety**

Aim 1: The primary outcome will be the difference in maximum VO₂ consumption obtained from a cardiopulmonary exercise test at baseline, 3 months and conclusion of the study [Δ VO₂ consumption] between Kuvan®(sapropterin dihydrochloride) use versus not. Descriptive statistics (mean, standard deviation, median, inter-quartile range, and frequency distribution) will be calculated to summarize, at baseline, participants' demographic and medical history, and the primary outcome of interest (peak Vo₂) according to randomized intervention sequences. We will ensure a balanced randomization is accomplished using t or nonparametric (Wilcoxon's) tests whenever

each test's distribution assumption is appropriate. We will use the variants of statistical methods (t tests and linear models) specifically designed to analyze crossover clinical trials to assess changes in peak VO₂ in response to Kuvan®(sapropterin dihydrochloride) supplementation in addition to current best practices versus current best practices alone.

Secondary Aims: The CPET measures and molecular biomarkers will be analyzed using the same crossover analysis models for crossover clinical trials¹⁶.

Data storage and sharing see: Protocol Addendum: Information Privacy and Security Items and Safety

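### During daily dosing no visible rule stops study drug for suspected hypersensitivity or another clinically significant suspected drug-related event; the continuation rule excepts only symptomatic hypotension

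*Combined protocol and SAP*

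**What the plan says.** The rule is in the section Monitoring for Adverse Events (AEs): "if a subject experiences medical problems or hospitalization, the study medication will be continued unless complicated by symptomatic hypotension". For a drug that has been stopped, the next sentence says "it would be resumed once baseline clinical status is confirmed, assuming the event was not felt to be related to the study medication itself". Later in the same section, relatedness is graded: "If an event is possibly, probably or definitely related to the intervention, it will be classified as intervention-related". No dosing action is attached to that class.

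The screening visit has a stricter rule for the 10 mg/kg test dose, which is followed by one hour of observation. It opens "If at any point during this time period, the subject develops hypotension" and goes on to "hypoxemia (decrease in oxygen saturation to <90% on room air), or any evidence of an allergic reaction (pruritus, rash, hives" and further signs. Any of these ends participation.

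The baseline visit section lets Group 1 go from 10 to 20 mg/kg after the day-7 call only if no adverse effect has been seen. The section on protection against risk stops drug for pregnancy.

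On timing, the therapeutic risks section says: "Most hypersensitivity reactions occurred within several days of initiating treatment". On reporting, the informed consent section says "They will also be provided with a phone number through which adverse events should be reported", and the monitoring section says that at each contact "subjects are to notify study staff if they experience any change in their medical condition or medications". Staff also watch the electronic record for emergency visits and admissions.

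**The concern.** The continuation sentence is an instruction, not a silence. Its trigger, a medical problem, is unqualified, so rash, hives or angioedema without symptomatic hypotension fall within it when it is read as written. The same hives that end participation within an hour of the test dose would not stop drug on day 3 of daily dosing.

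What is at stake is participant safety. A clinician would very probably stop drug for frank anaphylaxis whatever the text says, but would have to depart from the protocol to do so unless symptomatic hypotension was present. The gap matters more for milder early signs such as itching or rash, where staff are likelier to follow the written rule and where another dose could be given.

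**Working it through.** The plan gives no figure on this point, so the check is to set every visible dosing instruction side by side and run cases through them.

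**Step 1: every visible rule that changes dosing.**
- Test dose (screening visit): hypotension, hypoxemia or allergic signs within one hour. Action: participation ends.
- Day-7 call (baseline visit, Group 1): any adverse effect. Action: the increase is withheld; nothing is said about the current dose.
- Medical problem or admission (AE monitoring): symptomatic hypotension. Action: exception to continuing.
- After a stop (AE monitoring): relatedness. Action: decides restart.
- Pregnancy (protection against risk). Action: stop.
- Event classed as intervention-related (AE monitoring). Action: none for dosing.

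During daily dosing this leaves two explicit stop triggers: symptomatic hypotension and pregnancy.

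**Step 2: cases.**
- Hives within an hour of the test dose: participation ends.
- Hives on day 3 of daily dosing, blood pressure normal: the test-dose rule no longer applies, the hypotension exception is not met, and the resumption sentence is not reached because nothing was stopped. Literal result: continue.
- Rash reported by a Group 1 subject at the day-7 call: the dose stays at 10 mg/kg. Literal result: continue.
- Anaphylaxis with symptomatic hypotension: the exception applies, and restart is barred if the event is felt to be related. Here the text works.

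The second and third cases are the gap.

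**Step 3: timing and dose.** The allergic stop criteria cover one hour after a single 10 mg/kg dose. The risk section points to several days, and the target daily dose is 20/10 = 2 times the test dose. The day-7 condition is written for Group 1 only.

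**Step 4: contact schedule, as context.** Group 1's first scheduled contact on drug is day 7. Group 2 is supplied at week 13 and next contacted at week 16: (16 − 13) × 7 = 21 days. If the week-13 visit moves by the permitted week and the call stays at week 16, the range is (16 − 14) × 7 = 14 to (16 − 12) × 7 = 28 days. If several days means up to 7 (an assumption), the whole Group 2 range lies beyond it. This bears on detection, so it supports better prompts. It does not measure the missing stop criterion.

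**Step 5: how wide a stop rule should be.** The risk section lists seven common reactions, each seen in at least 4% of patients. As an illustration, assume each occurs at exactly 4% and all are judged related. With full overlap, 4% are affected (0.04 × 30 = 1.2 subjects). With no overlap, 7 × 4% = 28% (0.28 × 30 = 8.4 subjects). Stopping for every suspected related event, with restart then barred, could therefore cost roughly 1 to 8 of 30 subjects for mostly mild complaints. A severity threshold is needed.

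**The case against.** The strongest reply is that the continuation sentence was meant for intercurrent illness. Drug effects are elsewhere called adverse reactions or side effects, and the resumption sentence makes sense only if the authors expected drug to stay off after a related event. Other safeguards exist: the day-7 condition, the reporting phone number, record alerts, investigator contact when a report suggests deterioration, and a team review of adverse events every 4 weeks. The comparator is standard care without placebo, so blinding is no obstacle to stopping.

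Much of this stands. A reader might infer that the protocol intends dosing through anaphylaxis; the resumption sentence points the other way, and the documents do not support that reading. A reader might also infer that reactions would go unnoticed; the reporting routes make that too strong. What does not stand is the step from intent to instruction. The resumption sentence operates only after a stop and supplies no reason to stop. The safeguards help an event reach the team but leave the dosing rule as it is.

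The package insert (Appendix C) or the addendum may carry discontinuation advice. The visible text mentions that the insert is attached but does not make it a dosing rule.

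**Conclusion.** The point holds as a missing stopping criterion that sits beside an affirmative instruction to continue. It is worth correcting because the protocol itself names the hazard, places it mostly in the first days of treatment, and already treats allergic signs as disqualifying after the test dose.

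Its size cannot be put as a number of expected harms: the documents give no hypersensitivity rate for this population, and neither the contact intervals nor the share of doses covered by the test-dose rule would measure it. The conclusion rests on the literal text of the visible protocol, so confidence is moderate. Advice in the unseen appendices or addendum could narrow the gap.

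Two stronger remedies might be inferred, and neither is supported. A stop for every suspected related event ignores severity. A stop for oxygen saturation below 90% from any cause would carry a test-dose criterion into a population with diastolic dysfunction, where COPD that is not oxygen-dependent is allowed.

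**What to change.** Replace the continuation sentence in Monitoring for Adverse Events (AEs) with wording to this effect:

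*Study drug continues through an illness or admission judged unrelated to it, unless symptomatic hypotension occurs. It is stopped permanently for suspected hypersensitivity (rash, hives, pruritus, angioedema or anaphylaxis without another evident cause). It is stopped for any other serious or clinically significant event that the investigator suspects is related to it. Mild expected side effects do not require stopping.*

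Keep the existing resumption sentence for all stops other than hypersensitivity. Add rash, itching, hives and swelling to the side-effect prompts in Tables 2 and 3, which now ask about fever, nausea, vomiting, diarrhea and rhinorrhea only.

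The cost is a protocol amendment with IRB review and possibly a few more discontinuations. Each affects 1/30 = 3.3% of the planned sample and, in a crossover, may lose that subject's within-person comparison. The relatedness judgment is already required, and no visit, call or test is added.
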